#### 6.1.8. Data Adjustments/Handling/Conventions

All collected data will be presented in listings. Data not subject to analysis according to this plan will not appear in any tables or graphs but rather in the data listings only.

Adverse events will be coded using the latest version of the Medical Dictionary for Regulatory Activities (MedDRA).

For TEAEs:

AD-ST-33.04 Effective date: 30-Jun-2017

Version 2.0 | Date 29-Oct-2020 | AD-PR-109.01 Effective date: 26-Jun-2017

Page 25 of 51

- If an AE with partial time occurs on the same day of the first infusion then the AE will be considered a TEAE.
- If an AE has missing date then the AE will be considered a TEAE.
- If partial dates of AE occur, the convention for replacing missing dates for the purpose of discriminate TEAE is as follows:
  - If just day is missing then the AE will be considered a TEAE when the mm/year of AE is the same of after the mm/year of the first infusion;
  - If just month is missing then the AE will be considered a TEAE when the year of AE is the same or after the year of the first infusion.

#### 6.1.9. COVID-19

A Coronavirus Disease 2019 (COVID-19) Continuity Plan has been written to mitigate the negative effects of the COVID-19 pandemic on the conduct of this clinical trial.

The impact of COVID-19 on this clinical trials and trial participants will be extensively described both in tables and listings and in the CSR.

The following aspects will be summarized when due to COVID-19:

- Changes to treatment dispensation
- Changes to treatment administration
- Changes to visit windows to accommodate delays for some assessments
- Protocol deviations
- Missing efficacy endpoints Missing visits

## 7. Study Patients and Demographics

## 7.1. Disposition of Patients and Withdrawals from the study

The number of patients for each of the following categories will be presented in a table:

- All Treated Population
- Evaluable Population
- Completed patients
- Withdrawn from the study after start of treatment

#### • Reason of early study termination

Percentages will be calculated using the number of patients in the All Treated Population.

The total number of screening failures and the reasons for screen failure will be presented in a separate table.

In addition, assignment to analysis populations, the study completion status, and the reason of withdrawal from the study, and the screening failures will be listed.

#### 7.2. Protocol Deviations

Protocol deviations will be identified and classified at the data review meeting.

Protocol deviations will be medically reviewed. Protocol deviations, especially related to occasional lack of adherence to the schedule of assessments or visit timings (primarily attributable to optimization in the clinical management of this fragile children population), will not be presented.

In particular, the following situations will not be considered as protocol deviations:

- Missing data if not occurring at 2 consecutive time points.
- A  $\pm$  5-minute difference in the timing of vital sign measurements during emapalumab infusion.
- A  $\pm$  10-minute difference in the timing of vital sign measurements after emapalumab infusion.

Relevant protocol deviations categorized as major and minor will be tabulated in a summary table. Individual major and minor protocol deviations will be listed by patient.

### 7.3. Demographics and Other Baseline Characteristics

Summary statistics for age, sex, race, country of origin, height, weight, and body surface area (BSA) will be presented.

The MAS features present at the time of diagnosis of the current episode, the overall level of MAS activity, the functional testing related to HLH if available, and the optional genetic testing results, if available will be tabulated.

This analysis will be conducted for the All Treated Population and for the EVAL Population.

The number and percent of patients reporting various medical histories, grouped by MedDRA SOC and preferred term (PT) will be tabulated for the All Treated Population.

All demographics and baseline characteristics will be displayed in the data listings.

AD-ST-33.04 Effective date: 30-Jun-2017

Version 2.0 | Date 29-Oct-2020 | AD-PR-109.01 Effective date: 26-Jun-2017 Page 27 of 51

## 7.4. Exposure and Drug Administration

Investigational product administration will be summarized in terms of the number of doses received, average dose and cumulative dose per kg, and duration of exposure, from the first dose to the last dose of treatment.

This analysis will be conducted for the All Treated Population.

Drug administration and infusion details will be listed by patient and presented for the All Treated Population.

## 8. Efficacy Analysis

## 8.1. Efficacy Analysis

The following binary efficacy endpoints will be described using counts, proportions, and exact Clopper-Person 95% CI:

- Patients achieving MAS remission by Week 8 after initiation of emapalumab treatment
- Patients for whom at any time during the study glucocorticoids can be tapered
- Patients who tapered steroids to ≤1 mg/kg/day of prednisone equivalent dose
- Patients withdrawn from the study due to lack of efficacy

The following time-to-event efficacy endpoints will be analyzed descriptively:

- Time to first MAS remission
- Time to achievement of permanent glucocorticoids tapering
- Survival time

Summaries will include for each observed time, the survival estimate, failure rate, number of events and the number of patients remaining, also called population at risk. The median, lower quartile and upper quartile estimates of time-to-event and their 95% CI will be tabulated in a separate table. A Kaplan–Meier graph will be presented for each time-to-event endpoint.

The efficacy analysis will be based on the All Treated Population. Efficacy analyses will be repeated for the EVAL Population.

## 8.2. MAS Clinical Signs and Symptoms

Descriptive summaries of the overall level of disease activity, clinical signs and symptoms by visit will be tabulated and patient-level data will be displayed in listing.

AD-ST-33.04 Effective date: 30-Jun-2017

Version 2.0 | Date 29-Oct-2020 | AD-PR-109.01 Effective date: 26-Jun-2017

Page 28 of 51

## 9. Safety and Tolerability Analysis

Safety will be evaluated from reported AEs, changes from baseline in clinical laboratory values, changes in vital signs, electrocardiogram (ECG), physical examination results, pregnancies, and emergence of anti-drug antibodies.

All safety analyses will be performed on the All Treated Population.

#### 9.1. Adverse Events

A summary table will present the number and percent of patients reporting:

- Any AEs
- Treatment-emergent AEs (TEAEs)
- Non-TEAEs
- Serious AEs (SAEs)
- TEAEs leading to study treatment withdrawal
- TEAEs resulting in death

The table will show the number of events for each category.

All AEs, TEAEs, and SAEs will be coded using the latest version of MedDRA.

Summaries of the incidence (number and percentage of patients reporting the TEAE and the number of the TEAE) of TEAEs will be displayed by:

- PT
- SOC and PT
- SOC, PT and maximum severity
- SOC, PT and relationship to study drug

TEAEs related to study drug will be displayed by SOC and PT in a separate table for readability.

Summaries of the incidence of non-TEAEs will be displayed by PT.

In the case of multiple occurrences of the same TEAE in the same patient, each patient will only be counted once for each PT. However, all multiple occurrences will be included in the number of events. In the summaries showing severity and relationship to the study drug, the event with the maximum severity or strongest relationship will be reported. If a

AD-ST-33.04 Effective date: 30-Jun-2017

Version 2.0 | Date 29-Oct-2020 | AD-PR-109.01 Effective date: 26-Jun-2017

Page 29 of 51

particular event is missing the severity and/or relationship, then the strongest possible severity or relationship will be assumed for analysis (severity = severe, relationship = related).

By-patient AE data listings with all AEs will be displayed. Adverse events that are not treatment emergent will be flagged.

# 9.1.1. Treatment-Emergent Adverse Events Leading to Study Treatment Discontinuation

The number and percentage of patients reporting the TEAE and the number of the TEAE leading to study treatment discontinuation, by SOC and PT will be tabulated for the All Treated Population.

By-patient data listing of TEAEs leading to study treatment discontinuation will also be provided, displaying details of the event(s) captured on the CRF.

#### 9.1.2. Deaths and Serious Adverse Events

Serious adverse events will be tabulated by:

- PT
- SOC and PT.

By-patient data listing of AEs with a fatal outcome will be displayed. Serious adverse events will be described in a separate listing.

#### 9.1.3. Infusion-related Reactions

The number and percentage of patients reporting IRRs and number of the events by PT will be tabulated in total and by maximum severity.

In the case of multiple occurrences of the same TEAE in the same patient, each patient will only be counted once for each PT. In the case of different severities of the multiple occurrences of the same IRR in the same patient, the worse severity will be used for analysis.

A by-patient listing of all IRR will be displayed.

#### 9.1.4. Infections

The number and percentages of patients reporting infections and number of events, displayed by MedDRA PT, and will be tabulated in total and by maximum severity.

A by-patient listing of all infections will be displayed with date of sampling, pathogen, source, type of investigation, result (positive, negative, numerical value and units), and the AE it was linked to.

AD-ST-33.04 Effective date: 30-Jun-2017

Version 2.0 | Date 29-Oct-2020 | AD-PR-109.01 Effective date: 26-Jun-2017

Page 30 of 51

## 9.2. Clinical Laboratory Evaluations

The number of patients with clinical laboratory values below, within, or above the normal range by time point and in relation to baseline will be tabulated for each clinical laboratory analyte (shift table). Denominator of the percentages will be the number of patients in the All Treated Population.

Clinical chemistry and hematology results will be presented in separate tables.

Urinalysis results will not be tabulated. Abnormalities in urinalysis results assessed as medically relevant will be recorded as AEs and analyzed as described in Section 9.1.

Pregnancy test results will be tabulated by visit.

All laboratory values will be displayed in the data listings and those that are outside the normal range will be flagged, along with corresponding normal ranges.

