### 12.3.1 Efficacy Data

Graphical and tabular summaries will be prepared for each of the MAS distinct features, e.g. *fever; splenomegaly; WBC; platelet counts; liver function test (in particular ALT/AST); fibrinogen; ferritin; LDH.*

For binary endpoints (MAS remission by Week 8, number of patients who taper glucocorticoids, number of patients who discontinue due to lack of efficacy), 95% confidence intervals will be calculated for proportions.

For time to event endpoints (time to MAS remission, time to achievement of glucocorticoids tapering and time to death), Kaplan-Meier curves will be calculated and summary statistics, such as medians, proportions event-free at various time points will be calculated and presented, and 95% confidence intervals calculated where possible.

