### 12.3.2 Safety Data

All data relating to safety will be listed and summarized using descriptive statistics.

AEs will be coded and tabulated by body system, and by individual events within each body system. AEs will also be tabulated by severity and relationship to the study medication. Summaries will also be produced of SAEs and AEs leading to withdrawal from the study.

For each clinical laboratory test, individual patient values will be listed and summarized and change from pre-treatment baseline values calculated and summarized. Summaries of marked abnormalities and shift tables will be tabulated for each laboratory test.

In addition, other exploratory analyses of safety data, including summaries for different subsets of patients, may be conducted.

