## 2.2. Study Endpoints

## 2.2.1. Safety Endpoints

The safety endpoints of this study include the following:

- Incidence, severity, causality and outcomes of adverse events (AEs) (serious and non-serious), with particular attention being paid to infections.
- Evolution of laboratory parameters, in particular complete blood count (CBC), liver function tests (LFTs), inflammatory markers (ferritin and C-reactive protein [CRP]), and coagulation parameters.
- Number of patients withdrawn due to safety reasons.

[figure not shown]

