## 11. Changes from Planned Analysis

The Safety analysis set coincides with the All Treated Population and it is not listed in the analysis populations section. The EVAL Population has been added to check the robustness of the efficacy results. The Per-Protocol analysis set has been removed due to the small sample size and the introduction of the EVAL population.

Infusion-related reaction has been added in the safety endpoints (Section 2.2.1).

AD-ST-33.04 Effective date: 30-Jun-2017

Version 2.0 | Date 29-Oct-2020 | AD-PR-109.01 Effective date: 26-Jun-2017

The glucocorticoids tapering endpoint has been modified when it is not possible to establish whether a patient have been treated for sJIA/AOSD or not before study start for all patients or when it is not possible to retrieve glucocorticoids dose administered before the occurrence of MAS for all patients who already are treated for sJIA/AOSD. In this case the endpoint is "Number of patients for whom, at any time during the study, glucocorticoids can be tapered by 50% (or more) of the dose administered at emapalumab treatment start.

IL-10, sCD163, TNFa and IL-18 may be analysed and/or reported separately.

The following have been added:

- safety patient profile reports (Section 12.1)
- descriptive summaries of neutralizing antibody in case of positive ADA results (Section 9.5.3)
- Number and percentage of patients who tapered steroids to  $\leq 1 \text{mg/kg/day}$  of the equivalent dose of prednisone (Section 6.1.7)

No other changes from the analyses specified in the protocol are planned.

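### At group level the SAP replaces the protocol's summaries of laboratory values, change from baseline and marked abnormalities with shift tables, and does not declare it

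*SAP*

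**What the plan says.** **Protocol.** Section 12.3.1 states that "Graphical and tabular summaries will be prepared for each of the MAS distinct features" and gives as examples fever, splenomegaly, WBC, platelets, liver function tests, fibrinogen, ferritin and LDH. Section 12.3.2 states that, for each laboratory test, "individual patient values will be listed and summarized and change from pre-treatment baseline values calculated and summarized". It then adds: "Summaries of marked abnormalities and shift tables will be tabulated for each laboratory test". Shift tables are therefore one of several outputs.

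**SAP.** Section 2.2.1 keeps the evolution of laboratory parameters, including ferritin and coagulation, as a safety endpoint. The opening of Section 9 says safety will be evaluated from, among other things, "changes from baseline in clinical laboratory values", and Section 6.1.7 defines change from baseline. Section 9.2, however, plans only patient counts, saying that "clinical laboratory values below, within, or above the normal range by time point and in relation to baseline will be tabulated", and otherwise lists all values with out-of-range flags. In Section 14.1 (Table 5) the laboratory tables are a chemistry shift table, a hematology shift table and pregnancy tests. In Section 14.3 (Table 7) the group figures are vital signs and Kaplan-Meier curves. Section 12.1 adds a plotted profile for each patient.

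Section 11 lists several departures from the protocol and closes with "No other changes from the analyses specified in the protocol are planned". The laboratory summaries are not among those departures. Neither the SAP errata nor the post-hoc analysis plan restores them.

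**The concern.** All endpoints are exploratory and the analysis is descriptive, so descriptive summaries are the main product of the study. Protocol 7.4 bases the efficacy evaluation on how cytopenias, liver function and coagulopathy evolve. A table with three categories records only whether a value crosses a limit of normal, not how far it moved. If it is the only group output, the clinical study report will contain no pooled figure for the size of the change in ferritin, LDH, transaminases, platelets or fibrinogen. A reader who trusts SAP 11 would also not know that protocol-specified summaries had been dropped.

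**Working it through.** **1. Protocol and SAP side by side (group level)**

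| Protocol output | SAP counterpart |
|---|---|
| Summary of laboratory values (12.3.2) | None listed |
| Summary of change from baseline (12.3.2) | Named in SAP 9, defined in 6.1.7, no table |
| Marked abnormalities (12.3.2) | None listed |
| Shift tables (12.3.2) | Present, titled chemistry and hematology |
| Table and graph of each MAS laboratory feature (12.3.1) | Shift tables only; no group laboratory figure |
| Splenomegaly (12.3.1) | Imaging in listings only (SAP 9.5.4) |
| Fever (12.3.1) | Covered by temperature summaries (SAP 9.3) and a figure |

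Two further signs suggest omission rather than decision. SAP 9.3 gives vital signs both actual values and changes from pre-dose, so the format was at hand. The errata to Section 6.1.8 add rules for values outside the quantification limits and tie them to the shift table, yet word them for descriptive statistics, for which no laboratory table exists.

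**2. Can a shift table stand in for the missing summaries? Ferritin**

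Inputs: the remission rule (Protocol 7.4, SAP 6.1.7) requires a fall of at least 80% from the higher of the screening and baseline values, or a value below 2,000 ng/mL, whichever is lower. Entry requires ferritin above 684 ng/mL (Protocol 4.1.1). The documents give no ferritin ULN, so 150, 300, 500 and 684 ng/mL are assumed.

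With starting value B, the remission limit is L = min(0.2 × B, 2,000). For any ULN below 2,000, L lies above normal when 0.2 × B > ULN, that is, when B > 5 × ULN.

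| Assumed ULN (ng/mL) | At the remission limit, still above normal if B exceeds (ng/mL) |
|---|---|
| 150 | 150 / 0.2 = 750 |
| 300 | 300 / 0.2 = 1,500 |
| 500 | 500 / 0.2 = 2,500 |
| 684 | 684 / 0.2 = 3,420 |

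Examples:
- B = 10,000: L = 2,000, a change of −8,000 (−80%). It reads above-to-above for every assumed ULN.
- B = 50,000: L = 2,000, a change of −48,000 (−96%). Again above-to-above for every assumed ULN.
- B = 2,000: L = 400. Above-to-above for ULN 150 or 300, above-to-within for 500 or 684.

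The result describes a patient at the limit; one whose ferritin falls further may move into the normal range.

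**3. LDH and ALT/AST.** Remission requires values below 1.5 × ULN. Anything above 1.0 and below 1.5 × ULN meets the rule and is still classed as above normal. For WBC and platelets, remission is set at the lower limit of normal, so a shift table does register that crossing, though not its size.

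**4. Fibrinogen.** It is a remission component and a named MAS feature. Protocol 8.4 treats coagulation as its own laboratory group, but SAP 9.2 and Table 5 name only chemistry and hematology. The profile in SAP 12.1 plots D-dimer and not fibrinogen.

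**The case against.** A reader might infer that the SAP gives no view of how ferritin and the other MAS parameters evolve. The documents do not support that. SAP 12.1 plots actual values by study day, from −14 to 70, for every patient: ferritin, CRP, triglycerides, ALT, AST, LDH, WBC, platelets, D-dimer and CXCL9. All values are also listed. With about 12 patients these plots are informative, and each ferritin fall can be read from them.

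Nor is response hidden from the efficacy results. Remission applies numeric thresholds and is reported as a proportion and as time to event, and the post-hoc plan adds a listing of the remission assessments.

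Three other inferences also go too far:
- Protocol 12.3.1 and 12.3.2 do not ask for by-visit summaries. The time-point element comes from SAP 9.2.
- Fever is not lost. Temperature is summarized and plotted, and the errata add presentation by route.
- It cannot be concluded that coagulation will go untabulated. SAP 9.2 refers to every analyte, fibrinogen might be filed under hematology or chemistry, SAP 12.1 allows laboratory tests to be added to the profile, and the table shells are a separate document not available here.

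Finally, no test, decision rule or sample size depends on these tables. All of this stands, and it limits the point to group-level reporting. None of it supplies the summarized values, change from baseline or marked abnormalities that Protocol 12.3.2 calls for, or explains why SAP 11 is silent.

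**Conclusion.** The point holds as a gap in group-level reporting and in the declared changes, and should be corrected. The comparison of planned outputs rests on the protocol, SAP, errata and post-hoc plan alone and is firm, except that unseen shells could place fibrinogen in one of the shift tables. The finding that shift tables cannot substitute rests on an assumed ferritin ULN: for any ULN below 2,000 ng/mL, a value at the remission limit shows no shift once the starting value exceeds 5 × ULN, which is 750 to 3,420 ng/mL over the assumed range of 150 to 684. How many of the roughly 12 patients this affects cannot be derived from the documents. The finding for LDH and ALT/AST needs no assumed ULN. The validity of the remission, tapering and survival analyses is not in question.

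**What to change.** In SAP 9.2, Table 5 and the figure list:
- Add descriptive summaries by time point (n, mean, SD, median, minimum and maximum, as SAP 4.1 already defines) of actual values and change from baseline for WBC, platelets, ALT, AST, LDH, ferritin and fibrinogen, with a group plot of each. The time-point layout is a recommendation that matches SAP 9.2; the summaries themselves are in the protocol.
- Add the marked-abnormality summaries and a spleen-size summary.
- State which table carries the coagulation tests.
- Keep the shift tables.

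In SAP 12.1, add fibrinogen to the patient profile. If any protocol summary is deliberately dropped, declare and justify it in SAP 11, and align the opening of SAP 9 with that decision. Fever needs no change.

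The cost is SAP wording plus a few tables and figures. The laboratory tests are scheduled at each study visit (Protocol 8.4) and spleen measurements every 2 weeks (Protocol 8.6.1), so no new data are needed.

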## 9.3. Vital Signs

Descriptive summaries of actual values by study day and time point will be calculated for systolic blood pressure (mmHg), diastolic blood pressure (mmHg), heart rate (bpm), oxygen saturation (%), and highest daily body temperature (Celsius).

During an infusion, day time points include:

- pre-dose assessment
- assessments during infusion at 15 minutes, 30 minutes, 45 minutes, 1 hour 15 minutes, 1 hour 30 minutes, 1 hour 45 minutes, and at the end of infusion and
- post-dose assessments at 1 hour, 2 hours, 3 hours, 4 hours, and 24 hours

For each infusion day, the post-infusion changes from pre-dose will be calculated and displayed in summary tables for systolic blood pressure (mmHg), diastolic blood pressure (mmHg), heart rate (bpm), oxygen saturation (%), and highest daily body temperature (Celsius). From infusion #2 onwards the table will show the following time points: pre-dose, end of infusion, and post-dose assessments at 1 hour, 4 hours, and 24 hours, if applicable.

All vital signs will be provided in data listings. For systolic blood pressure, any reduction of  $\geq$ 30% from baseline will be flagged.

